4.1.5. Handling of Missing and Incomplete Dates

In general, values for missing dates will not be handled unless methods for handling missing dates are specified in this section or relevant sections. The original reported dates collected on the eCRF should be used in all relevant listings. The following rules will be used for handling partial dates for analyses requiring dates.

When calculating the time since diagnosis of disease, a partial disease diagnosis date will be handled as follows in the calculation:

- If only the day is missing, then the first day of the month will be used.
- If both the month and day are missing, then 01 JAN of the year will be used.
- If the diagnosis date is completely missing, then the time since diagnosis will not be calculated.

When the date of the last dose is used in deriving variables such as duration of treatment or TEAE flag, a missing or partial date of the last dose will be handled as follows:

- If only the day is missing, then the earlier date of the last day of the month or the date that the participant discontinued treatment will be used.
- Otherwise, the date that the participant discontinued treatment will be used as the date of the last dose.

For relevant efficacy endpoints, a partial date of the death date will be handled as follows in the calculation:

- If mm/yyyy for the last known alive date = mm/yyyy for the death date, then the death date will be set to the day after the last known alive date.
- If mm/yyyy for the last known alive date < mm/yyyy for the death date, then the death date will be set to the first day of the death month.
- Otherwise, the partial death date will not be imputed.

4.2. Variable Definitions

The following variables will only be calculated if not reported on the eCRF.

4.2.1. Body Mass Index

Body mass index will be calculated as follows:

$$\text{Body mass index (kg/m}^2\text{)} = [\text{weight (kg)}] / [\text{height (m)}]^2.$$

4.2.2. Prior and Concomitant Medication

Prior medication is defined as any nonstudy medication started before the first dose of parsaclisib, placebo, or ruxolitinib.

Concomitant medication is defined as any nonstudy medication that is started accordingly:

- Before the date of first administration of parsaclisib, placebo, or ruxolitinib and is ongoing throughout the study or ends on/after the date of first study drug administration.
- On/after the date of first administration of parsaclisib, placebo, or ruxolitinib and is ongoing or ends during the course of study.

A prior medication could also be classified as "both prior and concomitant medication" if the end date is on or after first dose of parsaclisib, placebo, or ruxolitinib. In the listing, it will be indicated whether a medication is only prior, only concomitant, or both prior and concomitant.

For the purposes of analysis, all medications will be considered concomitant medications unless the medications can unequivocally be defined as not concomitant.

5. STATISTICAL METHODOLOGY

5.1. General Methodology

Unless otherwise noted, SAS® software (SAS Institute Inc, Cary, NC; v9 or later) will be used for the generation of all tables, graphs, and statistical analyses. Descriptive summaries for continuous variables will include but not be limited to the number of observations, mean, standard deviation, median, minimum, and maximum. Descriptive summaries for categorical variables will include the number and percentage of participants in each category.

A participant randomized to the placebo group may cross over to parsaclisib treatment if the participant meets the criteria for an early crossover defined in Protocol Section 4.1.3. Unless specified, efficacy and safety analyses for between-treatment comparisons (parsaclisib vs placebo) will be conducted using the data truncated at the time of treatment crossover for those participants who make an early treatment crossover.

Interim analyses are planned for this study as defined in Section 10.

5.2. Treatment Groups

This is a randomized, double-blind, parallel treatment group design. Participants will be summarized by treatment groups. A participant randomized to the control group may make a crossover to the active treatment before Week 24 if the participant met the criteria for an early crossover. Unless specified, efficacy and safety analyses for between-treatment comparisons (parsaclisib + ruxolitinib vs placebo + ruxolitinib) will be conducted using the data truncated at the time of treatment crossover for those participants who made an early treatment crossover before Week 24. Data collected after the treatment crossover will be summarized and tabulated separately without treatment comparisons.

5.3. Analysis Populations

5.3.1. Intent-to-Treat Population

All participants who are randomized will constitute the ITT population. Treatment groups for this population will be defined according to the treatment assignment at the time of randomization regardless of the actual study drug the participant might take during their participation in the study.

The ITT population will be used for the summary of demographics, baseline characteristics, participant disposition, and analyses of all efficacy data.

Participants with missing baseline assessments will be excluded from the ITT population for the responder analyses.

5.3.2. Per-Protocol Population

Participants in the ITT who are considered to be sufficiently compliant with the Protocol will compose the PP population.

The following procedures will be performed to identify those participants who are to be excluded from the PP population:

- Clinical review of Protocol deviations
- Clinical review of concomitant medications as defined in Section 6.8 of the Protocol
- Clinical review of the dose administration and drug accountability listing
- Clinical review of inclusion/exclusion criteria

Participants with missing baseline assessments will be excluded from the PP population for the responder analyses.

The determination of participants being considered for exclusion from the PP population by the clinical team will be prepared and signed before unblinding and database freeze.

The PP population will be used in the supportive sensitivity analyses for efficacy endpoints.

5.3.3. Safety Population

The safety population will include all participants who received at least 1 dose of parsaclisib, placebo, or ruxolitinib. Treatment groups for this population will be determined according to the actual treatment the participant received regardless of assigned study drug treatment.

All safety analyses will be conducted using the safety population.

6. BASELINE, EXPOSURE, AND DISPOSITION

[Appendix A](#) provides a list of data displays. Sample data displays are included in a separate document.

6.1. Demographics, Baseline Characteristics, and Disease History

6.1.1. Demographics and Baseline Characteristics

The following demographics and baseline characteristics will be summarized for the ITT population by treatment group: age, sex, race, ethnicity, weight, height, and BMI.

6.1.2. Baseline Disease Characteristics

The following baseline disease characteristics will be summarized for the ITT population by treatment group: ECOG performance status, neutrophils, platelets, hemoglobin, and leukocytes at baseline.

6.1.3. Disease History

6.1.3.1. Myelofibrosis Disease History

The time since diagnosis to randomization, current MF disease, prognostic factors, risk level as defined by DIPSS, a prior splenic irradiation was performed, if splenectomy was performed, and whether transfusion was received in the 12 weeks before randomization will be summarized for all participants in the ITT population by treatment group.

Time since diagnosis will be calculated as follows:

Time since diagnosis (years) = (date of randomization – date of diagnosis + 1) / 365.25.

The MF screening symptom individual and total scores will be summarized for the ITT population by the treatment group.

6.1.4. Prior Therapy

The number of prior systemic regimens for MF will be summarized for all participants in the ITT population by treatment group. The component drugs of prior systemic therapy regimens will be coded using the WHO Drug Dictionary. The number and percentage of participants who received each drug will be summarized by WHO drug class and WHO drug PT. The regimen name, route, dose, frequency, start and stop dates, and reason for discontinuation will be listed.

The number of participants who received prior radiation for non-MF related cancer treatment will be summarized for the ITT population by treatment group. The radiotherapy type, body site, start and stop dates, reason for regimen, total dose, number of fractions received, and best response will be listed.

The number of participants who had prior surgery or surgical procedure for non-MF related cancer treatment will be summarized for the ITT population by treatment group. The date and description of the surgery/procedure will be listed.

6.1.5. Medical History

For participants in the ITT population, medical history will be summarized by assigned treatment group. This summation will include the number and percentage of participants with significant medical history for each body system/organ class as documented on the eCRF.

6.2. Disposition of Participant

The number and percentage of participants who were randomized, who were treated, who were ongoing with study treatment, who discontinued study treatment with a primary reason for discontinuation, who were still in the study, and who withdrew from the study with a primary reason for withdrawal will be summarized for the ITT population by treatment group. The number of participants randomized by country and/or site will also be provided by treatment group.

6.3. Protocol Deviations

Protocol deviations recorded in the clinical trial management system will be summarized and listed.

6.4. Exposure

For participants in the safety population, exposure to parsaclisib, placebo, and ruxolitinib will be summarized descriptively as the following:

- **Duration of treatment with ruxolitinib (days):** date of last dose of ruxolitinib – date of first dose of ruxolitinib + 1.

- **Duration of treatment with parsaclisib/placebo (days):** date of last dose of parsaclisib/placebo – date of first dose of parsaclisib/placebo + 1.
- **Average daily dose of ruxolitinib (mg/day):** total actual ruxolitinib dose taken (mg) / duration of treatment with ruxolitinib (days).
- **Average daily dose of parsaclisib/placebo (mg/day):** total actual parsaclisib/placebo dose taken (mg) / duration of treatment with parsaclisib/placebo (days).

Total actual dose taken will be calculated based on the information entered on the Drug Exposure eCRF.

- **Total dose administered for ruxolitinib (mg):** total dose administered for each participant will be the sum of ruxolitinib administered across cycles.
- **Total dose administered for parsaclisib/placebo (mg):** total dose administered for each participant will be the sum of parsaclisib/placebo administered across cycles.

6.5. Study Drug Compliance

For participants in the safety population, overall compliance (%) for parsaclisib and ruxolitinib will be calculated for all participants as follows:

$$\text{compliance (\%)} = 100 \times [\text{total dose actually taken}] / [\text{total prescribed dose}].$$

The total prescribed dose is defined as the sum of the doses prescribed by the investigator accounting for dose modifications.

The total actual dose taken will be calculated based on information entered on the Drug Accountability eCRF. If there are dispensed drugs that have not been returned yet, the actual dose taken starting from the dispense date of the unreturned drugs will be imputed by the dose taken as reported on the Dosing eCRF.

6.6. Prior and Concomitant Medication

Prior medications and concomitant medications will be coded using the WHO Drug Dictionary. The number and percentage of participants in the ITT population for each prior and concomitant medication will be summarized by WHO drug class and WHO drug PT for each treatment group.

7. EFFICACY

[Appendix A](#) provides a list of data displays. Sample data displays are included in a separate document.

7.1. General Considerations

Unless otherwise stated, the strata identified in the randomization process will be used in all efficacy analyses. Within a platelet category, in the event that the study fails to enroll a sufficient number of participants in a particular DIPSS stratification level, at the time of final analysis for database lock, that stratification will be combined with the nearest adjacent DIPSS

level (eg, intermediate-1 vs intermediate-2 vs high). For example, if either intermediate-1 or high risk is too small (eg, fewer than 10 participants), it will be merged with intermediate-2. If intermediate-2 has too few participants (eg, fewer than 10 participants), then it will be merged with the smaller of the 2 adjacent strata. At the time of interim analyses, all DIPSS stratification levels will be combined if too few participants (eg, fewer than 10 participants) are enrolled in 1 DIPSS stratification level.

The ITT population will be used for all efficacy analyses unless otherwise stated.

7.2. Efficacy Hypotheses

The primary hypothesis is that the number of participants achieving $\geq 35\%$ reduction in spleen volume from baseline to Week 24 for parsaclisib plus ruxolitinib is not the same as the number of participants achieving $\geq 35\%$ reduction in spleen volume from baseline to Week 24 when compared with placebo plus ruxolitinib as measured by the odds ratio for response. The hypotheses of the study are as follows:

- H_0 (null hypothesis): $\theta_{PAR} = \theta_{PLB}$
- H_A (alternative hypothesis): $\theta_{PAR} \neq \theta_{PLB}$

7.3. Analysis of the Primary Efficacy Parameter

7.3.1. Primary Efficacy Analysis

The primary endpoint of this study is the proportion of participants with $\geq 35\%$ spleen volume reduction from baseline to Week 24 as measured by MRI (or CT scan in applicable participants). The primary endpoint will be analyzed by CMH test stratified by DIPSS category (intermediate-1 vs intermediate-2 vs high) and baseline (or screening, if applicable) platelet count ($\geq 100 \times 10^9/L$ vs 50 to $< 100 \times 10^9/L$ inclusive).

The baseline spleen volume will be measured by MRI (or by CT for applicable participants) during the baseline visit (Days -7 to 1); the last value will be used if there are multiple values measured during the baseline visit.

The Week 24 spleen volume will be measured by MRI (or by CT for applicable participants) during the Week 24 visit; the last value will be used if there are multiple values measured during the Week 24 visit. Missing values will not be imputed.

The percentage change from baseline to Week 24 will be calculated using the following formula:

$$\% \text{ change} = 100 \times [\text{Week 24 spleen volume} - \text{baseline spleen volume}] / \text{baseline spleen volume}$$

A participant will be considered as having achieved $\geq 35\%$ reduction of the spleen volume from baseline to Week 24, if the participant had both baseline and Week 24 spleen volume measurements, the participant did not make an early crossover to receive the active treatment (for ruxolitinib plus placebo participants) before the Week 24 visit, the percentage change from baseline was not missing, and the percentage change from baseline reduction was $\geq 35\%$.

A participant who had a missing Week 24 spleen volume, discontinued treatment before Week 24, or made an early crossover to receive parsaclisib plus ruxolitinib before the Week 24 visit will be considered as a nonresponder for the endpoint of $\geq 35\%$ reduction of spleen volume.

A participant who had a missing baseline assessment will be considered as nonevaluable.

At the time of interim analysis, a participant who was still on treatment, but has not followed up for the timepoint assessment and had no timepoint assessment, will also be considered as nonevaluable.

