3.3. Sample Size Considerations

The primary endpoint of this study is the proportion of participants with $\geq 35\%$ spleen volume reduction from baseline to Week 24 as measured by MRI (or CT scan in applicable participants). The primary endpoint will be analyzed by CMH test stratified by DIPSS category (intermediate-1 vs intermediate-2 vs high) and baseline platelet count ($\geq 100 \times 10^9/L$ vs 50 to $< 100 \times 10^9/L$ inclusive). Assuming a 58.2% (29.4%) response rate for participants with normal (low) platelet count for the ruxolitinib plus parsaclisib group versus 41.0% (17.2%) response rate for participants with normal (low) platelet count for the ruxolitinib plus placebo group, to achieve 83.67% power to detect a statistically significant difference with a 2-sided Type I error of 5%, a sample size of 440 participants is required to be randomized equally between treatment groups.

For the key secondary endpoint of proportion of participants who have a $\geq 50\%$ in MFSAF TSS from baseline to Week 24, assuming a response rate of 61.7% (50.0%) for participants with

normal (low) platelet count for the ruxolitinib plus parsaclisib group and a response rate of 45.9% (34.5%) for participants with normal (low) platelet count for the ruxolitinib plus placebo group, a sample size of 440 will provide 80.02% power using CMH test given a 2-sided Type I error of 5%.

A test for OS will be performed when 85 deaths are observed using the log-rank test stratified by platelet count and DIPSS category at baseline at a 2-sided Type I error level of 0.05. The log-rank test will provide 80% power to detect a hazard ratio of 0.54. Assuming a median survival time of 5.3 years for ruxolitinib plus placebo and enrollment duration is 1.5 years, the expected time to analysis from the first participant randomized is 3 years.

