7.3.2. Subgroup Analyses for Primary Endpoint

Subgroups will be formed based on the following participant characteristics and baseline variables for those participants whose data are available:

- Sex: male and female
- Age group: ≤ 65 years or > 65 years
- MF type: PMF or PPV-MF/PET-MF
- Presence/absence of V617F mutation at baseline
- Presence/absence of HMR mutations at baseline
- Baseline spleen volume group: \leq median or $>$ median
- Baseline spleen palpation size group: ≤ 10 cm or > 10 cm
- Race: White/Caucasian, Black/African-American, Asian, American-Indian/Alaska Native, Native Hawaiian/Pacific Islander, or other
- Ethnicity: Hispanic/Latino, not Hispanic/Latino, or other
- Platelet: $\geq 100 \times 10^9/L$ vs 50 to $< 100 \times 10^9/L$, inclusive using baseline platelet counts. Note that if a participant's platelet count is $< 50 \times 10^9/L$ at baseline, the platelet count at screening will be used for stratification/randomization.
- DIPSS: intermediate-1, intermediate-2, or high

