7.4.2.1.2. MFSAF v4.0 Total Symptom Score for Time-to-Event Endpoints

The MFSAF v4.0 TSS for baseline will be derived as the same way in Section [7.4.2.1.1](#). The daily postbaseline TSS will be calculated from Day 7 to the day before the Week 24 visit. The Day X TSS is the average TSS between Day $(X - 6)$ and Day X. For example, the TSS on Day 7 is the average of the TSS from Day 1 to Day 7. The missing individual score and the missing daily TSS will follow the rule defined in Section [7.4.2](#).

7.4.2.2. Proportion of Participants With a $\geq 50\%$ Reduction in MFSAF v4.0 Total Symptom Score

The difference between parsaclisib plus ruxolitinib and placebo plus ruxolitinib in the proportion of participants who have a $\geq 50\%$ reduction in TSS from baseline to Week 24 evaluated by MFSAF v4.0 will be assessed using CMH test stratified by baseline (or screening, if applicable) platelet count and DIPSS category at randomization for the ITT population as primary analysis and PP population as sensitivity analysis. In the case that there is an insufficient number of participants enrolled in any DIPSS level within a platelet category, the collapsing rule specified in Section 7.3.1 will be applied. Missing values will not be imputed.

The percentage change from baseline to Week 24 will be calculated using the following formula:

$$\% \text{ change} = 100 \times (\text{Week 24 total score} - \text{baseline total score}) / \text{baseline total score}.$$

A participant will be considered as having achieved $\geq 50\%$ reduction of the TSS from baseline to Week 24 if the participant had both baseline and Week 24 TSS, the participant did not make an early crossover to receive parsaclisib plus ruxolitinib before the Week 24 visit, and the percentage change from baseline was not missing and was $\leq -50\%$.

A participant who has a missing Week 24 TSS, discontinued treatment before Week 24, is unblinded prior to Week 24 for early crossover to parsaclisib plus ruxolitinib, or has a baseline value of 0 will be considered as having not achieved the $\geq 50\%$ reduction.

A participant who has a missing baseline assessment will be considered as nonevaluable.

At the time of interim analysis, a participant who is still on treatment, but has no timepoint assessment for TSS, will also be considered as nonevaluable.

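### The SVR35 and TSS50 tests are valid but not adjusted for baseline spleen volume or baseline TSS, which may forgo a modest amount of precision

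*SAP*

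**What the plan says.** For the primary endpoint, SAP 7.3.1 says: "The primary endpoint will be analyzed by CMH test stratified by DIPSS category"; platelet count is the other stratification factor. For the key secondary endpoint, SAP 7.4.2.2 says that the difference in proportions "will be assessed using CMH test stratified by baseline (or screening, if applicable) platelet count and DIPSS category at randomization". Protocol Table 17 matches both.

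Each analysis set is complete for its own baseline. SAP 7.3.1: "A participant who had a missing baseline assessment will be considered as nonevaluable". SAP 7.4.2.2 repeats the rule for TSS: "A participant who has a missing baseline assessment will be considered as nonevaluable".

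The baselines are used elsewhere:
- Each is the denominator of its percentage change.
- SAP 7.3.2 lists "Baseline spleen volume group" and a palpable spleen size group among the subgroups. Protocol 10.4.1 compares the arms within them, and SAP Appendix A plans CMH Tables 2.1.2.6 and 2.1.2.7 for this.
- A baseline TSS of 0 is counted as nonresponse (SAP 7.4.2.2).

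The visible supportive analyses of the primary endpoint are the per-protocol set, counting later responders among early crossovers (both SAP 7.3.3), and uncollapsed DIPSS levels (Protocol 10.4.1). None adjusts for baseline.

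**The concern.** Both endpoints cut a percentage change from a measured baseline at a threshold. Dividing by baseline does not by itself make response independent of baseline. If baseline spleen volume or TSS predicts response within the platelet and DIPSS strata, a model containing it estimates the treatment effect more precisely. It also corrects chance imbalance in that baseline. This matters most at the two interim looks, with about 50 and 110 participants per arm, where a false stop would end the trial. The data are already collected, and no evaluable participant would be lost. The choice has to be made before unblinding, because a covariate added afterwards carries little credibility.

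**Working it through.** **Inputs from the documents.** N = 440, 1:1, two-sided 5% (SAP 3.3). Assumed spleen response: 58.2% vs 41.0% with normal platelets, 29.4% vs 17.2% with low. Assumed TSS response: 61.7% vs 45.9% and 50.0% vs 34.5%. Stated power: 83.67% (spleen) and 80.02% (TSS). Continuation rules: Z > 0.18 at 100 participants, Z > 1.28 at 220, Z > 1.96 at 440 (SAP Tables 6 and 7).

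**Assumptions, not in the documents.** Low-platelet share f. R², the share of within-stratum response variance explained by baseline. The Week 12 effect equals the Week 24 effect, and the looks are correlated as if they used one outcome. Only an endpoint's own gates are counted for it. DIPSS strata are not modelled.

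**Step 1: reproduce the stated power.** With n_s per arm in stratum s and mean rate p̄_s, the expected final CMH Z is

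d = Σ (n_s/2)(p1_s − p0_s) / √[Σ (n_s/2) p̄_s(1 − p̄_s)].

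At f = 0.15 there are 33 low-platelet and 187 normal-platelet participants per arm.

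- Spleen: (16.5 × 0.122 + 93.5 × 0.172) / √(16.5 × 0.233 × 0.767 + 93.5 × 0.496 × 0.504) = 18.095/5.131 = 3.53.
- TSS: (16.5 × 0.155 + 93.5 × 0.158) / √(16.5 × 0.4225 × 0.5775 + 93.5 × 0.538 × 0.462) = 17.33/5.222 = 3.32.

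With no interim gates, power is Φ(d − 1.96), about 94% and 91%. That is not what SAP 3.3 states. Now require all three thresholds to be passed. The Z values are trivariate normal with means d√t, t = 100/440, 1/2 and 1, and correlations √(t_i/t_j). Power becomes 83.6% (spleen) and 79.3% (TSS). For f from 0.10 to 0.33, spleen falls from about 84% to about 82%, and TSS stays at 79 to 80%. The stated figures therefore appear to include both gates.

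**Step 2: calibrate.** Solving for d gives 3.531 (83.67%) and 3.351 (80.02%). The chance of passing both gates is then 85.8% (spleen) and 82.9% (TSS), which caps what a better final test can achieve.

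**Step 3: add adjustment.** An adjusted analysis multiplies the expected Z by 1/√(1 − R²). If only the final test is adjusted, the interim means stay the same and their correlation with the final Z is multiplied by √(1 − R²). The equivalent sample size is 440/(1 − R²).

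| R² | Spleen, all looks | Spleen, final only | TSS, all looks | TSS, final only | Equivalent N |
|---|---|---|---|---|---|
| 0 | 83.7% | 83.7% | 80.0% | 80.0% | 440 |
| 0.02 | 84.3% | 83.8% | 80.8% | 80.2% | 449 |
| 0.05 | 85.3% | 84.1% | 81.9% | 80.5% | 463 |
| 0.10 | 87.0% | 84.4% | 83.7% | 81.0% | 489 |
| 0.20 | 90.1% | 85.0% | 87.3% | 81.7% | 550 |

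**Step 4: check by simulation.** Spleen endpoint, 2,500 trials per row, f = 0.15, spleen gates only. CMH stratified by platelets against a logistic model with treatment, platelets and baseline:

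| Odds ratio per SD of baseline (R²) | CMH | Adjusted |
|---|---|---|
| 1.0 (0) | 83.4% | 83.5% |
| 0.8 (0.01) | 83.9% | 83.7% |
| 0.67 (0.035) | 83.0% | 84.2% |
| 0.5 (0.09) | 83.4% | 87.6% |
| 0.4 (0.15) | 84.2% | 89.3% |

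Under the null, final-test rejection was 4.6 to 5.7% for both methods, consistent with 5% within simulation error. The pattern agrees with Step 3, and no row shows a loss beyond simulation error.

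**The case against.** The best defence is that nothing here is wrong. A CMH test stratified by the randomization factors controls type I error and is the test used for the sample size. That stands.

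A reader might infer that the plan ignores baseline or keeps it out of every between-arm comparison. The documents do not support that: both baselines are denominators, and baseline spleen size defines planned CMH comparisons.

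A reader might also infer that precision is certainly being discarded. That needs baseline to be prognostic within strata, and the documents give no such association. The subgroup list is not evidence, since it also contains sex, race and ethnicity. The baseline-of-0 rule handles a percentage change that cannot be computed. Because both endpoints are already scaled by baseline, the remaining association could be small or nil. Gains equivalent to 8% or 14% more participants need odds ratios of 0.5 or 0.4 per SD. Those mean response of about 63% vs 30%, or 67% vs 25%, at 1 SD below and above the mean baseline. Nothing in the documents supports gradients that steep.

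Two practical objections stand and shape the fix. SAP 7.1 anticipates DIPSS levels with fewer than 10 participants, so a model at n = 100 may meet sparse cells. SAP 7.2 frames the hypothesis as an odds ratio, and a covariate-conditional odds ratio is not the same quantity as the CMH common odds ratio.

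None of this removes the low-cost case for prespecifying an adjusted analysis. Parts of the SAP are redacted, so an adjusted exploratory analysis cannot be excluded.

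**Conclusion.** The point holds as an efficiency improvement. Neither visible responder analysis adjusts for its own baseline, and that baseline is complete in the evaluable set. Whether this costs anything depends on a prognostic strength that the documents do not give.

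The gain is nil at R² = 0. At R² of 0.05 to 0.10 with all looks adjusted, it is 1.6 to 3.3 points for spleen and 1.8 to 3.7 for TSS, so about 2 to 4. Adjusting the final test alone yields 0.4 to 0.9 points, because the two gates cap power. These sizes rest on the Week 12 and Week 24 effects being equal and on each endpoint facing only its own gates.

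The figures should not be read as a demonstrated loss of power in this trial, or as a reason to doubt a CMH result.

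**What to change.** In SAP 7.3.1, SAP 7.4.2.2 and Protocol Table 17, prespecify before unblinding:

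- **Model.** Logistic regression with treatment, the randomization strata collapsed by the SAP 7.1 rule, and log baseline spleen volume for SVR35. For TSS50, use untransformed baseline TSS, since zero is possible. Protocol 10.4.1 collapses below 30 participants and SAP 7.1 gives 10 as its example, so align them.
- **Effect measure.** A standardised difference in proportions with a 95% CI, with a statement that this is not the odds ratio of SAP 7.2.
- **Role.** Either the adjusted model is the main analysis and CMH the sensitivity analysis, or CMH stays the formal test and the adjusted model is the prespecified source of the estimate and CI.
- **Interim looks.** If the adjusted test is the formal test, use it at both Week 12 looks in SAP Section 10 as well, because most of any power gain arises there. Name CMH as the fallback if the model does not converge.

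The cost is SAP and Protocol wording, one further model per endpoint, a slightly more complex analysis and a changed effect measure. No new data are needed.
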